6.1.1 TAK-659/Ixazomib Dose Adjustments for Hematologic Toxicities

Blood counts should be regularly monitored during the study as specified in the Schedule of Events and tested more frequently if clinically indicated based on local standard practice. Comparison to baseline values and AE grading based on CTCAE (v.5) will be performed. When severe hematological AE's occur (\geq Grade 4 events, febrile neutropenic infection, thrombocytopenia with signs of overt bleeding or clinically significant bleeding), close monitoring and medical management using supportive care if indicated will be given based on standard practice (See Section 6.3) while the study drug should be continued. If these events persist despite supportive care (not resolved to \leq Grade 1, or baseline, or a level considered acceptable by the investigator within 7 days), at the investigator's discretion, bone marrow aspirate assessment will be performed to evaluate whether the prolonged myelosuppression is due to leukemic infiltration or disease progression. If leukemic blasts are $\leq 5\%$ in bone marrow and

bone marrow aplasia is seen, the study drugs should be continued for completion of the current cycle if less than 14 days, with repeat bone marrow aspirate in the absence of peripheral hematologic recovery to assess marrow cellularity. In the absence of evidence for bone marrow recovery, the study drugs should be withheld for up to 21 days. Clinical and laboratory re-evaluation should be repeated at least weekly or more frequently until recovery to \leq Grade 1 or baseline or a level considered acceptable by the investigator. Upon recovery, TAK-659 may be reinitiated (along with Ixazomib) at the same dose level or at a reduced dose level at the discretion of the investigator. If no recovery occurs within 21 days (based on peripheral blood counts and/or repeat bone marrow aspirate) after the study drug hold (42 days in total after the first dose on Cycle 1, Day 1), the patient should discontinue study treatment, and if this occurs in Cycle 1, the patient will be considered to have a DLT. The patient will continue to be followed until resolution or stabilization of the event, initiation of another anti-leukemia therapy, or overt AML progression, whichever occurs first.

When a dose reduction of TAK-659 or ixazomib is required in a patient, no re-escalation of dose will be permitted.

6.1.2 TAK-659 dose modifications for Nonhematologic Toxicities

Please refer to the Table below for dose held and dose reduction recommendations for non-hematologic toxicities. When the dose of TAK-659 is withheld based on the following criteria, clinical and laboratory re-evaluation should be repeated at least weekly or more frequently until the toxicity resolves to \leq Grade 1, or baseline, or a level considered acceptable by the treating investigator (must be \leq Grade 2). Upon recovery, TAK-659 may be reinitiated either at the same dose level or at a reduced dose level. For events in which there are transient lab value abnormalities that, based on investigator assessment, are not clinically significant or related to disease and not the drug, continuation of therapy without following the dose modification guideline is permissible after discussion with the sponsor investigator.

Criteria	Action
All Grade 3 Nonhematologic Toxicities with the exception of:	
 • Hold TAK-659 until resolution to Grade \leq 1 or baseline or a level considered acceptable by the investigator (must be \leq Grade 2). 
 ◦ If resolved in \leq 7 days, then maintain the dose level. ◦ If resolved in $>$ 7 days, then dose reduce by 1 dose level. ◦ If recurs, then dose reduce by 1 dose level. • For the exceptions listed, maintain dose level (no dose hold required). • Permanent discontinuation should be considered if the toxicities persist as \geq Grade 3 for more than 21 days despite temporary disruption of study drug.
Grade 4 Nonhematologic Toxicities	
 • Permanently discontinue TAK-659 for any grade 4 nonhematologic toxicities that are at least possibly related to TAK-659.

In general, the study drug(s) will resume only after the resolution of AEs to \leq Grade 1 or baseline or as specified in these dose modification guidelines. However, retreatment with study drug(s) could start when the AEs are resolved to a level deemed acceptable by the investigator. When a dose reduction of TAK-659 is required, no re-escalation of dose will be permitted.

6.1.3 Ixazomib Dose Adjustments for Hematologic Toxicities

Ixazomib Dose Adjustments for Hematologic Toxicities	
Criteria	Action
Within-Cycle Dose Modifications In Induction (< 2 cycles and marrow blasts present)	
 Dose reduction is not required
Within-Cycle Dose Modifications In consolidation (after documentation of morphologic blast clearance, generally beginning after the second cycle)	
 See below

 If platelet count $\leq 20 \times 10^9/L$ or ANC $\leq 0.20 \times 10^9/L$ on a ixazomib dosing day (other than Day 1) 	
 Ixazomib dose should be withheld. Complete blood count (CBC) with differential should be repeated at least twice weekly until the ANC and/or platelet counts have exceeded the prespecified values. Upon recovery, ixazomib may be reinitiated with 1 dose level reduction.
Dose Modifications for Subsequent Treatment Cycles	
 Delay of 1 week in the start of a subsequent cycle due to lack of toxicity recovery as ANC $< 0.5 \times 10^9/L$, platelet count $< 30 \times 10^9/L$ Hold ixazomib until resolution as per criteria Upon recovery, reduce ixazomib 1 dose level. The maximum delay before treatment should be discontinued will be 2 weeks or at the discretion of the PI.
Dose Modifications for Subsequent Treatment Cycles	
 All hematologic toxicities For hematologic toxicity that occurs during a cycle but recovers in time for the start of the next cycle,: 
 If dose was reduced within the cycle, start the next cycle at that same dose. If due to toxicity timing, ie, after Day 15 dosing thus a dose reduction was not required at that point in the cycle, reduce ixazomib by 1 dose level at the start of that cycle. Do not reduce the dose both within a cycle and at the start of the cycle for the same most severe toxicity.

Ixazomib Treatment Modification (Delays, Reductions, and Discontinuations) Due to Adverse Events (Non-Hematologic Toxicities)		
Adverse Event (Severity)	Action on Study Drug	Further Considerations
Peripheral Neuropathy: Grade 1 peripheral neuropathy	
 • No action 	Grade 1 signs and symptoms: asymptomatic; without pain or loss of function; clinical or diagnostic observations only [27]
New or worsening Grade 1 peripheral neuropathy with pain or Grade 2	
 • Hold study drug until resolution to Grade ≤ 1 or baseline 	Grade 2 signs and symptoms: Moderate symptoms; limiting instrumental activities of daily living (ADL) [27]
New or worsening Grade 2 peripheral neuropathy with pain or Grade 3	
 • Hold study drug until resolution to Grade ≤ 1 or baseline • Reduce study drug to next lower dose upon recovery 	Grade 3 signs and symptoms: severe symptoms; limiting self-care ADL; assistive device indicated [27]
New or worsening Grade 4 peripheral neuropathy	
 • Discontinue study drug 	
Grade 2 Rash	
 • Symptomatic recommendations as per section 6.3 	The investigator and project clinician may discuss considerations for dose modifications and symptom management.
Grade 3 nonhematologic toxicity judged to be related to study drug	
 • Hold study drug until resolution to Grade < 1 or baseline 	Symptomatic recommendations noted in Section 6.3
If not recovered to $<$ Grade 1 or baseline within 4 weeks	
 • Reduce study drug 1 to next lower dose upon return to $<$ Grade 1 or baseline 	
Subsequent recurrence Grade 3 that does not recover to $<$ Grade 1 or baseline within 4 weeks	
 • Hold study drug until resolution to Grade < 1 or baseline • Reduce study drug to next lower dose 	Monitor closely, take appropriate medical precautions, and provide appropriate symptomatic care
Grade 4 nonhematologic toxicities judged to be related to study drug	
 • Consider permanently discontinuing study drug 	Exceptions are cases in which the investigator determines the patient is obtaining a clinical benefit

Once ixazomib is reduced for any toxicity, the dose may not be re-escalated.

6.2 Dose Levels for Dose Reduction

Dose level	Dose of TAK-659 Days 1-15	Dose of Ixazomib Days 1, 8, 15		
Starting Dose	100mg po once daily	2.3 mg	3mg	4mg
Dose level (-1)	80mg po once daily	Contact sponsor-investigator for consideration of schedule below 2.3mg.	2.3mg	3mg
Dose level (-2)	60mg po once daily	--	Contact sponsor-investigator for consideration of schedule below 2.3mg.	2.3mg.
If study drug dosing is delayed for >21 days despite supportive treatment per standard clinical practice or more than 2 dose reductions are required in a patient, this patient will have study treatment discontinued.				

6.3 Management of Clinical Events

Therapies that are required to manage AEs and control cancer symptoms are allowed based on standard clinical practice, unless specifically excluded. Supportive care agents, such as erythropoietin, G-CSF, blood products (RBC and platelet transfusions), and pain medications are permitted as needed per American Society of Hematology (ASH)/ASCO guidelines or local institutional practice. However, these agents should not be used in this study in a manner that would either help establish eligibility for the study or support escalation of study drug dose during dose escalation.

6.3.1 Prophylaxis Against Infection

Patients with advanced hematological malignancies may be at an increased risk of infection. Prophylactic use of antibiotic, antiviral, or antifungal medication can be considered as clinically indicated and as per local standard practice. Ciprofloxacin is considered a standard for patients with ANC <500. Antifungal prophylaxis with fluconazole or isovuconazole which are a moderate CYP inhibitory agents is permitted with dose reduction of TAK-659 as in 5.3.1. Patients requiring prophylaxis with fluconazole or patients whom develop active fungal infection, continuation of TAK-659 in the combination will require dose reduction to 60mg po daily of the TAK-659 with the mold-active agent isovuconazole, and careful analysis of toxicity parameters, especially including QTc and hepatic and pancreatic enzymes. Dosing of Ixazomib will not require modification in the absence of relatable toxicity. The above determined TAK-659 dose cannot be escalated. If toxicity supervenes, the patient will be taken off study for alternative anti-infective therapy as needed. Should no toxicity be observed in a cohort, stepwise dose escalation, first to 80mg, may be considered.

Antiviral therapy such as acyclovir may be initiated as clinically indicated.

The severe and prolonged period of neutropenia seen with therapy is frequently associated with neutropenic fevers and a high risk of infection with bacteria or fungi and viral reactivation. To minimize

the risk of infection, it is recommended that patients be placed on “neutropenic precaution”, with or without the addition of prophylactic antibiotics, antifungals, or antivirals. In addition, patients should be screened for possible infectious foci (eg, dental status).

The components of “neutropenic precaution” while inpatient may vary by institution but most commonly include: a high efficiency particulate air-filtered room, a diet free of raw berries or vegetables grown in dirt, no sick visitors, and no smoking. In addition, hand washing by all visitors and caregivers should be strictly enforced.

Consideration should be given to antibiotic, antifungal, and antiviral prophylaxis during therapy, either as an outpatient or as an inpatient; however, the use of such agents should be at the discretion of the treating physician based on the local standard practice. Patients who develop neutropenic fever should be evaluated promptly and treated immediately with parental antibiotics tailored to the prominent organisms and resistance patterns of the institution.

Patients with lymphopenia and neutropenia may be more prone to developing infections, such as respiratory tract infections or pneumonia. Consider a diagnosis of opportunistic infection including *Pneumocystis jirovecii* pneumonia (PJP, formerly known as *Pneumocystis carinii* pneumonia) in patients presenting with shortness of breath, cough, or fever. Prophylaxis for PJP may be initiated (either at baseline or during treatment) if clinically indicated. For older patients, patients with recent exposure to steroids or immunosuppressive agents, or patients who, in the investigator’s opinion, are more susceptible to opportunistic infection at baseline, PJP prophylaxis should be considered at the start of the study treatment. When steroids and/or any immunomodulatory agents need to be used to manage the AEs during the study, PJP prophylaxis should be considered when the study treatment resumes or is coadministered. Trimethoprim-sulfamethoxazole is recommended as the treatment of choice for PJP prophylaxis unless contraindicated. However, investigator discretion in selecting a more appropriate prophylaxis regimen for their patients is permitted.

Myelosuppression can also be associated with reactivation of herpes zoster, cytomegalovirus (CMV), herpes simplex and other viruses. Antiviral therapy such as acyclovir, gancyclovir, valacyclovir, or other antiviral agents may be initiated as clinically indicated. Testing of CMV replication by a local polymerase chain reaction (PCR) assay will be required at baseline, and further monitoring and prophylactic or preemptive therapy to asymptomatic patients, if indicated, should follow the institutional standard practice. The following agents should be considered for prophylaxis or preemptive treatment against CMV: ganciclovir intravenously (IV), valganciclovir (orally), foscarnet (IV), or cidofovir (IV). Duration of antiviral therapy generally is for at least 2 weeks until CMV is no longer detected by PCR. Institutional guidelines may be used in the management of viral reactivation.

6.3.2 Leukocytosis

For patients who develop symptoms of leukocytosis (WBC $> 100,000/\text{mm}^3$) while on the study, TAK-659 treatment should be withheld until the leukocytosis symptoms are controlled. Treatment of leukocytosis symptoms may include leukapheresis and hydroxyurea administration (concurrent use of hydroxyurea with the study drug is only permitted during the first 21 days of study treatment) per institutional guidelines. When the WBC of the patient is $< 50,000/\text{mm}^3$ and symptoms are improved, TAK-659 treatment may be restarted after consulting with the project clinician.

6.3.3 Prophylaxis Against Risk of Reactivation of Herpes Infection

Patients may be at an increased risk of infection including reactivation of herpes zoster and herpes simplex viruses. Antiviral therapy such as acyclovir, valacyclovir, or other antivirals may be initiated as clinically indicated. Other antivirals are also acceptable.

6.3.4 Pneumonitis

Patients with serious lung events that do not respond to conventional antimicrobial therapy should be assessed for drug-induced pneumonitis after ruling out infectious causes and alternative etiologies. If pneumonitis is suspected, TAK-659/Ixazomib treatment should be interrupted and the patient treated per standard of care. If pneumonitis is moderate/severe, discontinue TAK-659/Ixazomib. Patients should be monitored for respiratory signs and symptoms throughout treatment and be advised to promptly report respiratory symptoms.

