5.2 Phase Ib Dose Escalation

Dose escalation will involve only Ixazomib, increasing from 2.3 mg and then to 3 mg. Patients in each cohort will continue to the completion of the second cycle, and undergo evaluation of toxicity/tolerability prior to consideration of dose-escalation to the next cohort. The maximal dose of Ixazomib at 4mg was determined as in aforementioned myeloma studies.

Dose Cohort	Number of patients	TAK-659 (PO) Days 1-15	Ixazomib (PO) Days 1, 8, 15
1	3-6	100 mg, once daily	2.3 mg
2	3-6	100 mg, once daily	3 mg
3	3-6	100 mg, once daily	4 mg

Patients within each cohort will be followed for toxicity occurring within the first 2 cycles prior to initiating a dose/schedule escalation of the individual drugs in the next cohort, in context of the type of dose limiting toxicity (DLT) observed and to what study drug(s) the toxicity is related.

In cohort 1, If 1/3 patients develop grade ≥ 3 DLT toxicity, then 3 more patients will be entered at this dosing level; if $< 2/6$ patients develop DLT, then the next cohort will involve escalation of Ixazomib in dose.

If, on the other hand, toxicity attributable to the combination is seen in the first cohort at ≥ 2 patients, then we will consider modification of the protocol to reduce the initial dose of TAK-659 and/or Ixazomib. Again, our prior experience involving the addition of pharmacodynamically-active dosing as starting to a combination of Sorafenib and Vorinostat suggest we will not see this reduction as necessary. The dose modification plan will be based on the nature of the DLT:

Dose Cohort	Number of patients	TAK-659* (PO) Days 1-15	Ixazomib* (PO) Days 1, 8, 15
1	3-6	100 mg, once daily	2.3 mg
Dose modification plan			
		80 mg, once daily	2.3 mg Contact sponsor-investigator for consideration of schedule below 2.3mg.

*On clinic days for PK determination, TAK-659 will be taken first and then Ixazomib.

In cohort 2, if 1/3 patients develop grade ≥ 3 DLT toxicity, then 3 more patients will be entered at this dosing level; if < 2/6 patients develop DLT, then the next cohort will involve escalation of Ixazomib in dose.

Dose Cohort	Number of patients	TAK-659* (PO) Days 1-15	Ixazomib* (PO) Days 1, 8, 15
2	3-6	100 mg, once daily	3 mg
Dose modification plan based on the nature of DLT			
If DLT at least possibly related to TAK-659 OR not related to Ixazomib			
		80 mg, once daily	3 mg
If DLT at least possibly related to Ixazomib OR not related to TAK-659			
		100 mg, once daily	2.3 mg

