5.2.2 Dose Reduction or Discontinuation in the setting of Pneumonitis

Should the patient develop grade 1 or 2 pneumonitis, the combination therapy will be held until the episode resolves and the TAK-659 and Ixazomib doses will undergo 1-step reductions, respectively. If the episode recurs the patient will be taken off study. Similarly, should the patient develop grade 3+ pneumonitis, permanent drug discontinuation will be required.

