6.1 Dose Delays/Dose Modifications

All toxicities that occur during the study will be actively managed following the standard of care unless otherwise specified in the protocol.

Patients who have the TAK-659 dose held due to treatment-related or possibly related AEs may resume study drug after resolution of the AE but may either maintain the same dose level or have doses of TAK-659 reduced (dose reduction) by at least 1 dose level. When a dose reduction occurs, the TAK-659 dose will be reduced to the next lower dose that either been established as a safe dose during dose escalation or is lower by a 20-mg increment. If initial dose adjustment does not provide sufficient relief, the dose of TAK- 659 can be further reduced if the treating physician considers that the patient is benefiting from study treatment and may benefit at a further reduced dose of TAK-659. When a dose reduction of TAK-659 is required due to toxicity, no dose re-escalation will be permitted.

If TAK-659 dosing is delayed for > 21 days for TAK-659-related or possibly related toxicities despite supportive treatment per standard clinical practice or more than 2 dose reductions are required in a patient, this patient should be considered to have study treatment discontinued, unless the treating physician considers that the patient may benefit from continued study treatment after resolution of AEs

to \leq Grade 1, or baseline, or a level considered acceptable by the physician. The patient will continue to be followed for 30 days for safety evaluation after the last administration of TAK-659.

Patients who experience a DLT (during escalation) or DLT-like toxicity (during phase 2 of the study) during the first cycle will, in general, require that treatment with TAK-659 be permanently discontinued. If, in the opinion of the investigator it is in the patient's best interest to continue treatment with TAK-659, then the dose of TAK-659 will be reduced by at least 1 dose level when treatment resumes after recovery of the toxicity or toxicities in question to \leq Grade 1 or to baseline values or to a level considered acceptable by the investigator. However, if a patient requires a dose delay of > 21 days for such an event to resolve despite the best supportive care permissible per protocol, then the patient must be discontinued from the study.

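### Section 6.3.4 stops both drugs for moderate or severe pneumonitis without giving a CTCAE grade; if moderate means Grade 2, it conflicts with Section 5.2.2 on re-exposure after a first Grade 2 episode

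*Combined protocol and SAP*

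**What the plan says.** Two sections of the combined protocol and SAP deal with pneumonitis by name.

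Section 5.2.2 is graded. For the milder grades: "Should the patient develop grade 1 or 2 pneumonitis, the combination therapy will be held until the episode resolves". Then "the TAK-659 and Ixazomib doses will undergo 1-step reductions, respectively. If the episode recurs the patient will be taken off study". For the higher grades: "should the patient develop grade 3+ pneumonitis, permanent drug discontinuation will be required". It sits under the parent heading "5.2 Phase Ib Dose Escalation", but its text names no phase.

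Section 6.3.4, among the event-management guidance in Section 6.3, is not graded. It covers suspicion first: "If pneumonitis is suspected, TAK-659/Ixazomib treatment should be interrupted and the patient treated per standard of care". The next sentence is: "If pneumonitis is moderate/severe, discontinue TAK-659/Ixazomib". It gives no route back to treatment and does not mention 5.2.2.

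Section 6.1 has a separate rule for TAK-659. A DLT or DLT-like toxicity "during the first cycle will, in general, require that treatment with TAK-659 be permanently discontinued". If the investigator judges that continuing serves the patient best, "then the dose of TAK-659 will be reduced by at least 1 dose level when treatment resumes".

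**The concern.** Section 6 has adverse events graded by CTCAE v5, yet the stopping sentence in 6.3.4 uses plain severity words. A site that takes *moderate* to mean Grade 2 would stop both drugs after a first Grade 2 pneumonitis. A site that follows 5.2.2 would wait for resolution and give both drugs again at a lower dose.

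What is at stake is re-exposure after a possible drug-induced lung injury. Section 1.4.7.1 lists pneumonitis as a potential risk of TAK-659 and reports five serious cases, all considered possibly related to the drug. In a multicenter trial, whether a patient is re-exposed should not depend on which section the site consults.

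**Working it through.** The plan states no figure on this point and no arithmetic applies. The check sets the two rules side by side for a first episode, reading *moderate* as Grade 2 and *severe* as Grade 3.

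| First episode | Section 5.2.2 | Section 6.3.4 | Result |
|---|---|---|---|
| Suspected, grade not yet known | not addressed | interrupt both drugs | no conflict |
| Grade 1 | hold, then resume each drug one step lower | interrupt | no conflict |
| Grade 2 | hold, then resume each drug one step lower | discontinue both | conflict |
| Grade 3 or higher | permanent discontinuation | discontinue both | agree |

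The Grade 2 row depends on two readings.

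1. *Moderate* as Grade 2. The protocol pairs this word with a grade only in the peripheral neuropathy rows of the ixazomib non-hematologic table (Section 6.1.3). There Grade 2 is described as moderate and Grade 3 as severe. The scale is borrowed from another toxicity, and usage is not uniform: Section 6.1.1 uses *severe* for hematologic events of Grade 4 or higher. If 6.3.4 meant *moderate* as Grade 3, the Grade 2 row shows no conflict.
2. *Discontinue* as a final stop. Section 6.3.4 uses a different word, *interrupted*, for the temporary stop in the sentence before. Section 6.3.2, on leukocytosis, says when TAK-659 may be restarted; 6.3.4 says nothing of the kind. A final stop is therefore the natural reading, though not the only possible one.

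The next question is whether another rule resolves the Grade 2 row.

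- Section 6.1, general hold rule: TAK-659 held for a related or possibly related event may resume after resolution, at the same or a lower dose, with no grade or cycle limit. This leans toward 5.2.2. It covers TAK-659 only and is not specific to pneumonitis. It also allows the same dose, which 5.2.2 does not.
- Section 6.1.2, closing paragraph: a general default that study drug or drugs resume once events settle. This also leans toward 5.2.2 and is also not specific to pneumonitis.
- Section 6.1, cycle 1 DLT rule: usually ends TAK-659 but allows a reduced dose on the investigator's judgment. It permits either outcome.
- Toxicity tables: the TAK-659 table in 6.1.2 covers Grades 3 and 4. The Grade 2 rows of the ixazomib table concern neuropathy and rash.
- The 21-day limits on delay or interruption (Sections 6.1, 6.2 and 6.4) do not help when an episode resolves sooner.

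The general defaults favor hold-and-resume, but they do not displace an instruction written for pneumonitis itself.

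Finally, the effect on DLTs. Section 5.4 counts a related non-hematologic toxicity of Grade 2 or higher that needs either dose reduction or discontinuation. A related Grade 2 pneumonitis within the first two cycles is a DLT under both rules, so the count does not change.

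**The case against.** The strongest reply is that 5.2.2 is the dedicated, graded section on dosing in pneumonitis, while 6.3.4 is work-up and monitoring advice without dose levels. A site looking for the Grade 2 action finds it stated explicitly in one place only. Section 6.3.4 also opens with serious lung events that have not improved on antimicrobials, so its severity words may describe the worse end of the range, in line with the Grade 3 threshold in 5.2.2. Elsewhere the protocol often adds the word *permanent* when it means a final stop, and 6.3.4 does not. The general rules in 6.1 and 6.1.2 point the same way as 5.2.2.

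Much of this stands. It makes the conflict conditional, and it rules out the inference that no other provision bears on the question. It does not remove the problem: 6.3.4 still names both drugs, uses a word that the protocol elsewhere ties to Grade 2, and tells sites to discontinue. Nothing says which section prevails.

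A reader might also infer from the parent heading that 5.2.2 applies to phase I only. The documents do not support that firmly. Its text has no phase limit, and Section 6.3.1 relies on the neighboring antifungal dosing rule (under the number 5.3.1) as general guidance. If 5.2.2 were limited to phase I, phase II would have 6.3.4 alone and no conflict within that phase, but the two phases could then follow different rules.

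**Conclusion.** The concern holds in a conditional form. With *moderate* read as Grade 2 and *discontinue* as final, Sections 5.2.2 and 6.3.4 give opposite instructions on resuming both drugs after a first Grade 2 pneumonitis. With *moderate* read as Grade 3, they agree and 6.3.4 lacks only a grade label. The text does not settle which was meant, so confidence is medium, but either reading calls for the same edit.

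The extent is one cell of the table: a first episode, at Grade 2, on the question of re-exposure. How often it would arise cannot be estimated; the five serious cases in Section 1.4.7.1 are reported without grades, and Section 6.1 calls TAK-659-related pneumonitis rare.

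A reader might infer that the inconsistency disturbs dose escalation or the phase II toxicity boundaries. It does not: DLT counts, sample size and decision rules are the same under either rule. This is a patient-safety wording issue that should be corrected, not a design flaw.

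**What to change.** Replace the ungraded stopping sentence in Section 6.3.4 with one CTCAE v5 rule, stated for phase I and phase II, and make 5.2.2 match it or refer to it:

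- Suspected pneumonitis: interrupt both drugs.
- First Grade 1 or 2 episode: hold both drugs until resolved, then resume each one dose level lower per Section 6.2, subject to the cycle 1 DLT rule in Section 6.1.
- Grade 3 or higher, or any recurrence: permanently discontinue both drugs.

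If the sponsor intends the stricter rule, limit hold-and-reduce in 5.2.2 to Grade 1 and discontinue both drugs permanently at Grade 2 or higher or on any recurrence.

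The cost is the wording of two short paragraphs and their cross-references. The DLT definition needs no edit.
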